I confirm that I have read and understand this protocol and I agree to conduct this clinical study in accordance with the design and specific provisions of the protocol, with the exception of a change intended to eliminate an immediate hazard to participants. Any deviation from the study protocol will be documented in the case report form.

I agree to promptly report to the applicable ethics boards any changes in the research activity and all unanticipated problems involving risks to human participants or others. Additionally, I will not make any changes in the research without prior ethics and sponsor approval, except where necessary to ensure the safety of study participants.

[name]

Name

Signature

31-Oct-2017

Date (dd-mmm-yyyy)

STUDY CONTACT DETAILS

Role	Contact Details
Principal Investigator	[name] – [contact] [name] / [contact]
Co-Principal Investigator	[name] – [contact] / [contact]
Research Coordinator	[name] – [contact] [name] / [contact]
Sponsor	University Health Network (UHN)

ABBREVIATIONS AND DEFINITIONS

[figure not shown]
Acronym / Abbreviation	Definition
AIDS	Acquired immune deficiency syndrome
ANI	Asymptomatic neurocognitive impairment
ART	Anti-retroviral therapy
cART	Combination anti-retroviral therapy
CBR	Community-based research
CRGT	Cognitive remediation group therapy
DBT	Dialectical behavioural therapy
HAD	HIV-associated dementia
HAND	HIV-associated neurocognitive disorder
HIV	Human immunodeficiency virus
MBCT	Mindfulness-based cognitive therapy
MBSR	Mindfulness-based stress reduction
MND	Mild neurocognitive disorder
PLWH	People living with HIV

PROTOCOL SYNOPSIS

Full Title	IN HAND - Cognitive remediation group therapy to improve older adults' ability to cope with HIV-Associated Neurocognitive Disorder (HAND): A pilot randomized, controlled trial
Short Title	IN HAND
Protocol No.	CTNPT 029
Study Duration	Enrollment period: Three months Study period: Six months
Sponsor	University Health Network
Number of Centres	3
Study Design	Pilot; Parallel design randomized, controlled trial
Primary Objective	To compare the feasibility and acceptability of cognitive remediation group therapy (CRGT) against an active control as psychosocial treatment for older HIV-positive adults who have been diagnosed with mild-to-moderate HAND
Secondary Objectives	To determine the fidelity of the cognitive remediation group therapy (CRGT) model.
Exploratory Objectives	
 1. Change in stress, anxiety, and coping from pretest to posttest (between groups) 2. Sustained use of brain training activities 3. Change in use of mindfulness strategies (between groups)
Sample Size	N = 16
Randomization	1:1 8 in the treatment group and 8 in the active control group
Study Population	HIV-positive people \geq 40 years of age who have been living with HIV for more than 5 years and who have completed neuropsychological testing, received a diagnosis of Mild Neurocognitive Disorder (MND)
Experimental Therapy Description	Cognitive remediation group therapy: 10 weekly 3-hour sessions; each session is comprised of 45 minutes of tablet-based cognitive training using PositScience, a 15-minute break, and 1.75 hours of Mindfulness-Based Stress Reduction (MBSR) with a 15-minute break halfway through the MBSR component.
Active Control	10 weekly 3-hour sessions with a 15-minute break at the end of each hour; each session is comprised of process-oriented facilitation using a mutual aid model (i.e., encouraging peer discussion of effects of HIV, aging, and cognitive impairment to identify and initiate coping strategies).
Duration of Study	Ten weeks
Outcome Measures	
Primary:
 
Feasibility: The sampling frame is approximately 100 people. The following targets (all based on a denominator of 100) would need to be met for a larger study to be considered feasible: $\geq 30\%$ of those contacted agree to participate, $\geq 25\%$ complete the pre-test, $\geq 20\%$ attend the first session, $\geq 16\%$ complete the full series and complete the post-test. Each participant must attend 80% (8/10) of the group sessions to be considered as completing the series.

	
Acceptability: The sampling frame will be described (i.e., age, gender, ethnicity, length of time living with HIV, length of HAND diagnosis, length of time since last HAND follow-up at St. Michael's Hospital) in terms of those who agree and decline to participate. For those who cancel participation in the study, the research coordinator will follow-up by phone to ascertain the reason for attrition and this will be described, if the participant agrees. Participants will complete a standardized satisfaction scale (i.e., the Helping Characteristics of Self-Help and Support Groups Measure) that will be complemented by questions about session length, number of sessions, activities used, and evaluation of facilitators.
 
Secondary:
 
Intervention fidelity: Facilitators of both study arms will submit weekly session reports. These reports will include checklists of the therapy components; use of an average 80% of components listed will be considered as good fidelity. These reports will also include open-ended questions about the sessions, including questions on group dynamics, challenges faced, and detail on activities used.
 
Exploratory:
 
 • Change in stress, anxiety, and coping. • Sustained use of brain training activities • Change in use of mindfulness strategies 
Scales/Questionnaires:
 
 • Anxiety in Cognitive Impairment and Dementia Scale • Coping Self-Efficacy Scale of Health Problems • HIV/AIDS Stress Scale • Five Facet Mindfulness Questionnaire—Short Form (FFMQ-SF)
Statistical Analysis	Depending on the nature of the exploratory results and the true sample size, non-parametric tests or a power analysis on the exploratory outcomes may be appropriate.

STUDY FLOW CHART

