2.2 Primary Objectives

- Determine if a 10-session CRG is feasible and acceptable to older adults with mild-to-moderate HAND.

Feasibility will be measured based on a sampling frame of approximately 100 people. The following targets (all based on a denominator of 100) would need to be met for a larger study to be considered feasible: $\geq 30\%$ of those contacted agree to participate, $\geq 25\%$ complete the Baseline Visit, $\geq 20\%$ attend the first session, $\geq 16\%$ complete the full series and complete the Follow-up Visit. Each participant must attend 80% (8/10) of the group sessions to be considered as completing the series. Similar targets have been set in other pilot studies of psychosocial interventions (Kazak et al., 2005; Ledderer et al., 2013). These targets are also set to ensure that the study feasibly lead to a larger trial, as support groups require a minimum four participants per session (Stewart, Usher, & Allenby, 2009). There is also a risk to intervention integrity and group cohesion if participants consistently miss multiple sessions, usually defined as more than two sessions in a time-limited program (Stewart, Usher, & Allenby, 2009).

For acceptability, the number of participants in the sampling frame will be reported. Those who consent to participate will be described (i.e., age, gender, ethnicity, length of time living with HIV, length of HAND diagnosis, length of time since last HAND follow-up at St. Michael's Hospital). For those who discontinue participation in the study, the research coordinator will follow-up by phone to ascertain the reason for attrition and this will be described, if the participant agrees. Participants will complete a standardized satisfaction scale (i.e., the Helping Characteristics of Self-Help and Support Groups Measure) that will be complemented by questions about session length, number of sessions, activities used, and evaluation of facilitators.

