3.7 Sampling and Recruitment

There are approximately 100 people currently in the sampling frame (see Appendix V). This should provide an adequate frame to recruit participants ($n = 16$), especially as there is little other treatment

available for HAND in Toronto (or elsewhere). We will initiate the trial with a minimum of 75% participant enrolment (n = 12, with n = 6 in the Experimental arm and n = 6 in the Active Control arm) if required.

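### The Synopsis and Section 2.2 state different primary objectives, and the study-wide feasibility targets measure neither CRGT alone nor CRGT against control

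*Combined protocol and SAP*

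**What the plan says.** The Protocol Synopsis (Primary Objective) is comparative: "To compare the feasibility and acceptability of cognitive remediation group therapy (CRGT) against an active control". Section 2.2 has one arm in view: "Determine if a 10-session CRG is feasible and acceptable to older adults with mild-to-moderate HAND". No other section reconciles the two.

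Section 2.2 then sets four targets that must be met for a larger study to count as feasible, "all based on a denominator of 100":

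- at least 30% "of those contacted agree to participate"
- at least 25% "complete the Baseline Visit"
- at least 20% "attend the first session"
- at least 16% complete the series (8 of 10 sessions) and the Follow-up Visit

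None of them names an arm. Part of the rationale given for the targets is that "support groups require a minimum four participants per session".

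Section 3.1 enrols 16, eight per arm. Section 3.7 allows a smaller start: "We will initiate the trial with a minimum of 75% participant enrolment", that is, six per arm. Randomisation follows the Baseline Visit (Sections 3.5 and 5.1). Section 10.1 plans descriptive statistics such as attendee counts and percentage satisfaction, and Section 10.4 reports results against the Section 2.2 targets. Neither mentions a split by arm, although the Synopsis marks two of its three exploratory objectives as between-group.

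**The concern.** The decision rule should follow from the primary objective. Here there are two objectives, one comparing arms and one about CRGT alone, and a rule that counts people over the whole study. Two of the four counts are taken before any arm exists. The other two could be split by arm but are not.

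The verdict on feasibility therefore depends on what happens in the control arm as much as in the CRGT arm, and the plan does not say how a reader should get from it to a statement about CRGT. Section 10.2 gives insight into the acceptability of the new arm as one reason for the sample size, so a CRGT-specific result is clearly wanted. The four-per-session minimum belongs to each group at each session, and a study-wide count of completers does not show whether it was kept.

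**Working it through.** **1. The plan's own figures.** 2 × 8 = 16 enrolled; 0.75 × 16 = 12 at the minimum start. On a denominator of 100 the targets are 30, 25, 20 and 16 people. These reproduce the plan.

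**2. Which targets can differ by arm.** Agreement and Baseline Visit completion precede randomisation, so they cannot. First-session attendance and completion follow it, so they can.

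**3. Post-randomisation targets against the sample size.**

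- First session: 20 needed, 16 enrolled. Not reachable, and so not reachable with 12.
- Completion: 16 needed. With 16 enrolled this is 16/16. With 12 it is not reachable.

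**4. One control non-completer at N = 16.** If CRGT is 8/8, the completion target is still missed when at least one of eight controls fails to complete. The probability is 1 − p⁸, where p is an assumed control completion rate:

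| p | 1 − p⁸ |
|---|---|
| 0.80 | 83% |
| 0.90 | 57% |
| 0.95 | 34% |

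**5. When a weak CRGT arm could be hidden.** If every control completes, the fewest CRGT completers that still give 16 in total is 16 minus the number of controls:

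| Randomised | CRGT completers needed |
|---|---|
| 12 (6+6) | 16 − 6 = 10 of 6: not reachable |
| 16 (8+8) | 16 − 8 = 8 of 8 (100%) |
| 20 (10+10) | 16 − 10 = 6 of 10 (60%) |
| 25 (12 or 13 in CRGT) | 3 of 12 or 4 of 13 (25% to 31%) |

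With assumed true completion of 60% in CRGT and 95% in control, the chance of 16 or more completers is 1% at 8+8, 51% at 10+10 and 95% at 12+12. Masking needs at least 17 randomised.

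**6. Four per session.** Let X ~ Bin(n, a) be the number present, with n in the arm and a an assumed attendance probability, independent across people and sessions. The chance of at least one session in ten below four is 1 − (1 − P(X ≤ 3))¹⁰.

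- n = 6, a = 0.9: P(X ≤ 3) = 0.0159; over ten sessions 15%
- n = 6, a = 0.8: P(X ≤ 3) = 0.0989; over ten sessions 65%
- n = 6, a = 0.7: over ten sessions 95%
- n = 8, a = 0.8: P(X ≤ 3) = 0.0104; over ten sessions 10%

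**7. Precision by arm (Clopper-Pearson 95%).** 8/8: 63% to 100%. 7/8: 47% to 99.7%. 5/8: 24% to 91%.

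**The case against.** Section 2.2 uses the targets to judge whether a larger study is feasible, and a larger randomised trial needs both arms to run, so study-wide counts suit that question. That is fair, and it is a reason to keep study-wide figures. It does not make them a measure of CRGT feasibility or of a difference between arms, which are the two objectives as written.

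A reader might infer that pooling lets a failing CRGT arm pass. At the planned size it does not: 16 completers of 16 are required, so any non-completer in either arm misses the target. Nor can 13 of 16 be treated as a pass because 16/20 is 80%. That ratio is not a criterion in the plan, whose 80% figures concern one person's session attendance and fidelity components. On the stated denominator, 13 completers are 13%, below 16%.

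A reader might also infer that the trial cannot answer either question. That is too strong. Satisfaction is rated by participants about their own group in sessions 5 and 10, reasons for attrition are recorded, and attendance must be kept to apply the 8-of-10 rule. By-arm tables could be made; the plan simply does not commit to them or say how they bear on the conclusion.

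On group size, 80% is the plan's minimum for a completer, not an expected average, and independence is an assumption. At eight per arm the risk is modest. The larger figures apply to the fallback start of six, so they show a gap in measurement and do not predict failure.

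**Conclusion.** The point stands in this form: the two statements of the primary objective conflict, and the feasibility rule measures neither. At N = 16 the rule errs towards failure. The first-session target cannot be met, and one control non-completer defeats the completion target whatever CRGT achieves. At 12 the completion target carries no information about CRGT. Masking of a weak CRGT arm is a risk only if 17 or more are randomised, which the plan does not intend, although its own first-session target of 20 implies it. The four-per-session minimum is cited as a basis for the targets and measured by none.

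The counts rest on the fixed denominator of 100 in Section 2.2; if the number actually contacted were used instead, the head counts would change. The probabilities in steps 4 to 6 rest on assumed completion and attendance rates and on independence. The wording conflict and the missing by-arm summary rest on the text alone. This should be corrected, at the cost of wording only.

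**What to change.** - **Synopsis and Section 2.2:** state one primary objective, the feasibility and acceptability of CRGT, with the control arm described alongside.
- **Section 2.2:** keep agreement and Baseline Visit completion as whole-sample measures. Reconcile the study-wide targets of 20 and 16 people with N = 16 and the minimum start of 12.
- **Section 10.4:** report by arm first-session attendance, completion (8 of 10 sessions plus the Follow-up Visit), satisfaction, and the number of sessions with at least four attendees. Give exact 95% intervals for the proportions, over the number randomised to that arm. Base the statement about CRGT feasibility on the Arm 1 results, descriptively.

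A new pass mark of 7 of 8 (or 5 of 6) should not be added. At a true completion rate of 80% it would be met with probability 8 × 0.8⁷ × 0.2 + 0.8⁸ = 0.50 (or 6 × 0.8⁵ × 0.2 + 0.8⁶ = 0.66), so it would discriminate poorly and be easier to pass when recruitment falls short.

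The cost is protocol wording. The completion rule already requires attendance data, and no participants or visits are added. The downside is imprecision: with eight per arm, even 7/8 has an interval of 47% to 99.7%, so neither a firm CRGT verdict nor a formal comparison can be supported.

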1. INTRODUCTION, BACKGROUND, AND STUDY RATIONALE

1.1 Background

Cognitive impairment is a significant co-morbidity for people aging with Human Immunodeficiency Virus (HIV). It is estimated that approximately 50% of the aging HIV-positive population will be affected by HIV-Associated Neurocognitive Disorder (HAND) (Greene et al., 2015; Grant et al., 2014). HAND is diagnosed in three forms based on Frascati criteria: (a) **Asymptomatic Neurocognitive Impairment (ANI)** – evidence of neuropsychological impairment in at least two cognitive domains but no evidence of functional impairment or difficulty with daily functioning; (b) **Mild Neurocognitive Disorder (MND)** – evidence of impairment in at least two cognitive domains and evidence of subtle but significant functional daily impairments or difficulty with daily functioning (e.g., with work or in social situations); and (c) **HIV-Associated Dementia (HAD)** – evidence of marked impairment in several of all cognitive domains and evidence of significant functional daily impairments or difficulty with everyday functioning and activities of daily living (Antinori et al., 2007). If untreated, HIV-infected persons may progress through these stages in rapid succession as shown by high rates of HAD prior to the introduction of successful Combination Anti-retroviral therapy (cART) (Monforte et al., 2004). With the development and widespread use of modern cART, and the trend towards earlier treatment initiation, HAND is now less common and less severe, although still exists (Grant et al., 2014). It is of particular concern in the Acquired Immune Deficiency Syndrome (AIDS) survivors – those who are currently aging with HIV, and who frequently were treated with incompletely suppressive antiretroviral regimens, medications that had higher rates of mitochondrial toxicity, and often after an AIDS defining illness or when the immune system was very weak (Antinori et al., 2013; Hopcroft et al., 2013). It is characterized by problems with cognition, memory deficits, difficulties in processing new information, impairment in executive function, errors in problem solving, poor decision making, etc (Spudich, 2013). This in turn leads to stress, anxiety, social isolation, difficulty coping, and may impact every day functioning such as adherence to medication and paying bills. (Tedaldi, Minniti, & Fischer, 2015). HAND is thought to result from structural damage in the fronto-striatal-thalamic circuits in the brain, and hence there is no cure (Heaton et al., 2010) Strategies such as a switch to cART combinations with better central nervous system penetration have not been successful (Heaton et al., 2010; Monforte et al., 2004). With the addition of the cognitive decline of normal aging, HAND symptoms may become more apparent, further impairing the aging HIV-infected adult's ability to cope (Eaton, Craig, & Wallace, 2017; Hopcroft et al., 2013).

Psychosocial interventions have been studied in the general aging population with cognitive impairment and depression with the goal to decrease stress and depression and improve coping, daily functioning, and quality of life. Given success of these interventions in that setting, a similar approach might be useful to mitigate HAND's impact. However, research in this area is limited and most reports have studied only small cohorts, in diverse populations, and the optimal intervention type is unclear (Illa et al., 2014; Tedaldi, Minniti, & Fischer, 2015). Psychosocial factors (i.e., social networks, spirituality, mood) have been found to be significant predictors of the ability to cope with HAND when demographic variables (i.e., gender, age, educational level, and ethnicity) and neurocognitive variables (i.e., test scores) are controlled for (Cody et al., 2016). Cognitive remediation therapy training is developed to improve cognition in particular domains (like memory or speed or reasoning) or more globally (Cody, Fazeli, & Vance, 2015; Vance et al., 2010). The delivery of such training varies widely from person training with pen and paper or computer programs to group activities which may also be enhanced with exercise and nutritional advice. Cognitive remediation therapy has been found to decrease HAND-related stress and anxiety amongst middle-aged and older adults living with HIV (Cody, Fazeli, & Vance, 2015; Vance et al., 2010).

1.2 Selection of HAND Intervention Model

St. Michael's Hospital hosts a NeuroAIDS Research Program within their Neurobehavioural Research Unit. This program has been in operation for many years, and is the only site for gold standard neuropsychological HAND testing in Toronto, Ontario, Canada. People living with HIV who are concerned about thinking and memory problems are referred by their physician to this program for 3-4 hours of neurocognitive evaluation by a clinical neuropsychologist. As this is a research program, HAND-diagnosed participants are given the option of consenting to participate in further research.

The ideal HAND intervention model has yet to emerge. Brain training games have shown promise in people with HAND, especially in studies from [name] at the University of Alabama at Birmingham. There are many options for psychosocial group therapy that have been tested in the general population with dementia and depression (e.g., Mindfulness-Based Stress Reduction (MBSR), Mindfulness-Based Cognitive Therapy (MBCT), and Dialectical Behavior Therapy (DBT)) (Gu, Strauss, Bond, & Cavanagh, 2015). These mindfulness interventions have demonstrated promising outcomes in reducing stress and anxiety, and improving coping. Although these strategies have not been fully tested in HAND, they could have similar benefit. To determine the components of the novel intervention in this trial, we interviewed six HAND researchers from the United States, Canada, Spain, and Australia. These conversations indicated that: a) initiating brain training software in a group setting would be a novel strategy that could improve uptake and use (PositScience by BrainHQ was the preferred software); and b) MBSR may be the most suitable group therapy to complement the brain training software (see more details below). The combination of brain training games and MBSR fits within the category of Cognitive Remediation Group Therapy (CRGT), according to these expert informants. Additionally, we held two focus groups in Toronto – one of community leaders who are aging with HIV (n=10) and one of service providers working in the field of HIV (predominantly social workers, n=8). These focus groups were held to ascertain the community's opinion on: a) the ideal brain training software out of a short list (i.e., PositScience by BrainHQ, Lumosity, or Elevate); b) the ideal group therapy (i.e., MBSR, MBCT, DBT); b) the logistics of the novel intervention arm (i.e., setting, time of day, length of each session); c) a study name brainstorm; and d) the questionnaires' language and ideal method of completion (i.e., in-person with a coordinator, online). Focus group attendees agreed with the expert informants that PositScience by BrainHQ was the most compelling option for a brain training game, based on personal use experience, existing literature, and the software's ability to be used on all devices (i.e., computer, tablet, phone). The focus groups also identified that weekday afternoons may be the ideal time, and that three hours per session (with a break each hour) is a suitable length. The method of administering the questionnaires (see section nine) and the study's title (IN HAND) were decided directly from the focus group feedback.

Brain training games from PositScience by BrainHQ have been associated with improved self-report in people with MND when focused on specific domains (such as executive functioning or speed-of-processing), however most work to date has provided this software to individuals in their homes with relatively low uptake. Uptake is especially low among those who have more severe cognitive impairment.

Mindfulness-Based Stress Reduction (MBSR) is currently being examined in people with MND in a trial at the University of California, San Francisco's Memory and Aging Center ([name], in communication). This study is showing some promising preliminary feasibility and acceptability. At this site, MBSR is delivered in a group therapy format for eight weekly 2-hour sessions. It is facilitated by regulated health professionals (i.e., social worker and a nurse) and includes meditation, deep breathing, yoga, and talk therapy activities.

Our study will blend brain training with MBSR in a group environment in an attempt to improve uptake of the PositScience activities and the emotional coping strategies that can emerge from MBSR. MBSR was selected instead of MBCT or DBT as: a) it can be delivered in fewer sessions (the current guideline for DBT is a minimum 20 sessions); and b) MBSR is focused more on adaptive management as

opposed to the crisis-oriented behavior change that MBCT and DBT seek to impact. In the community and provider focus groups, MBSR was favored over the MBCT and DBT options. This combined focus on practical and emotional tools could show promise as a feasible, acceptable intervention model that can be tested in a larger trial.

